Because orthostasis was detected more frequently in FLOMAX capsule-treated patients than in placebo recipients, there is a potential risk of syncope (WARNINGS).

Abnormal Ejaculation Abnormal ejaculation, ejaculation failure, disorder, retrograde ejaculation and ejaculation decrease. Withdrawal from these clinical studies of FLOMAX capsules because of abnormal ejaculation was also dose-dependent with 8 of 492 patients (1.6%) in the 0.8-mg group, and no patients in the 0.4-mg placebo groups discontinuing treatment due to abnormal ejaculation.

Post-Marketing Experience Allergic-type reactions such as skin rash, angioedema, tongue, lips and face and urticaria have been reported positive rechallenge in some cases.

OVERDOSAGE

Should overdosage of FLOMAX capsules lead to hypotension (See WARNINGS and ADVERSE REACTIONS), support of the cardiovascular system is of first importance. Restoration of blood pressure and normalization of heart rate may be accomplished by keeping the patient in the supine position. If this measure is inadequate, then administration of intravenous fluids should be considered. If necessary, vasopressors should then be used and renal function should be monitored and supported as needed. Laboratory data indicate that tamsulosin HCl is 94% to 99% protein bound; therefore, dialysis is unlikely to be of benefit.

One patient reported an overdose of thirty 0.4-mg FLOMAX capsules. Following the ingestion of the capsules, the patient reported a severe headache.

DOSAGE AND ADMINISTRATION: FLOMAX capsules 0.4 mg once daily is recommended as the dose for the treatment of the signs and symptoms of BPH. It should be administered approximately one-half hour following the same meal each day.

For those patients who fail to respond to the 0.4-mg dose after two to four weeks of dosing, the dose of FLOMAX capsules can be increased to 0.8 mg once daily. If FLOMAX capsules administration is discontinued or interrupted for several days at either the 0.4-mg or 0.8-mg dose, therapy should be started again with the 0.4-mg once daily dose.

HOW SUPPLIED: FLOMAX capsules 0.4 mg are supplied in density polyethylene bottles containing 100 or 1000 hard gelatin capsules with green opaque cap and orange opaque body. The capsules are imprinted on one side with "Flomax 0.4 mg" and on the other side with "BI 58."

APPENDIX F**Lab Procedures****Four Glass Test - Procedure**

Participant Test Schedule: (Screening Visit #1): 4 glass urine microscopy and culture

(Visit #4 - Week 6): 4 glass urine microscopy and culture

1. Instruct participant to retract foreskin (if uncircumcised).
2. Wipe head of penis with one alcohol pad.
3. Collect the first 10 ml sample (**VB1**) directly into sterile container. (Range 5 - 30 ml)
Centrifuge, examine and culture as described below.*
4. Collect midstream sample (**VB2**).
Dip VB2 for pH, glucose and protein. Record results
Centrifuge, examine and culture as described below.*
5. **EPS** - Prostatic massage
 - a.) Collect EPS on a sterile surface. (Example: lid of urine cup)
 - b.) Estimate volume of EPS in μL . (1 drop \sim 50 μL)
 - c.) Examine 5 μL at 400X power.
Count WBC's, RBC's, hyphae.
 - d.) Place 10 μL on sheep blood agar (5%) of a urocult paddle and incubate at 37°C for 5 days. Record results at 48 hours and five days.
 - e.) If it grows, replate colonies on MacConkey agar for identification.
 - f.) Store any remaining volume of EPS in 1.0 - 1.5 ml cryovials.
 - g.) Snap freeze in liquid Nitrogen for later storage at -70°C.
6. Collect first 10 ml sample post massage (**VB3**) within 30 minutes. (Range 5 - 30 ml)
Centrifuge, examine and culture as described below.*

* **VB1, VB2 and VB3 SPECIMENS**

- a.) Centrifuge 2-3 mls of urine for five minutes.
- b.) Examine at 400X power.
- c.) Count WBC's, RBC's, hyphae (average of three fields rounded to nearest whole number.)
- d.) Place 100 μL of specimen on sheep blood agar (5%) plate and 100 μL of specimen on MacConkey agar plate.
- e.) Culture at 37°C for 5 days. Record results at 48 hours and five days.

* **Chlamydia trachomatis PCR**

- a.) Participant must not have urinated in the previous two (2) hours.
- b.) Collect 10 to 50 mL of first catch urine into a clean, empty plastic cup without preservatives.
- c.) Cap the specimen cup and label appropriately.
- d.) The following is a list of molecular tests to be used:
 - Geneprobe LCR
 - Abbott LcX,
 - Roche PCR (Cobas)
 - Becton-Dickinson

Uroflow and Post Void Residual Procedure

Participant Test Schedule: (Screening Visit #2)
(Visit #4 – Week 6- **PVR ONLY**)

1. Instruct participant to have a full bladder for this test. A minimum volume of 150 cc's constitutes a valid test. This can be assessed by ultrasound of the bladder.
2. Record three values -

Total Volume (ml)
Peak Flow (ml/second)
Mean Flow (ml/second)

Semen Sample Procedure

Participant Test Schedule: (Screening Visit #2)
(Post Clinic Visit #4*)

1. Instruct participant to remain abstinent for a minimum of two days.
2. Collect specimen in a sterile urine cup.
3. Measure volume in mls.
4. Plate 100 μ L on sheep blood agar (5%) plate and 100 μ L on MacConkey agar. Culture at 37°C for 5 days. Record results at 48 hours and 5 days.
5. Allow sample to stand at room temperature for thirty minutes.
6. Centrifuge for five minutes.
7. Aliquot seminal plasma into 1.0 - 1.5 ml cryovials.

Peroxidase Staining Procedure:

Prepare Benzidine-Cyanosine stock solution:

1. Dissolve 62 mg Benzidine (Sigma cat. # B3383) in 24 ml Methanol using a 100ml-graduated cylinder.
(Have 200ml of deionized H₂O boiling in a beaker. Dip 100ml graduated cylinder into boiling water, 30 seconds at a time, until benzidine is dissolved)
2. Add 75 mg Cyanosine (Phloxine B, Sigma cat. #P2759).
3. Add 26 ml boiling deionized or triple distilled H₂O.
4. Filter using Whatman #4 paper filter.

5. Store in brown bottle (solution is light sensitive) at room temperature for no more than 1 year.

Immediately prior to counting sample, make Benzidine-Cyanosine working solution:

1. Combine 1 ml Benzidine-Cyanosine stock solution (swirl vigorously before using) and 4 ul 3% H₂O₂.
2. Mix semen and Benzidine-Cyanosine working solution in 1:1 ratio (typically 20 ul each).
3. Place 20 ul of combination on a hemacytometer or slide with cover slip.
4. Scan slide under microscope at low power to assure even distribution of cells.
5. Count number of WBC per 5 high power fields (400X) after 5 minutes. WBC will be stained (pink/red) brown. Round cells which are not WBC (immature spermatids) will not be stained brown. The background will be pink.

- * Only for participants with localizing uropathogens at baseline visit #2 will provide semen sample 2-3 days after clinic visit #4.

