 - 3a) *Inflammatory chronic pelvic pain syndrome*, where white cells are found in the semen, expressed prostatic secretions (EPS), or voided bladder urine-3 (VB-3).
 - 3b) *Non-inflammatory chronic pelvic pain syndrome*, where white cells are NOT found in the semen, EPS, and VB-3.
4. *Asymptomatic inflammatory prostatitis* (AIP), where there are no subjective symptoms but white blood cells are found in prostate secretions or in prostate tissue during an evaluation for other disorders.

Patients in Categories 1-3 are characterized by chronic pain; however, unlike patients in Category 1 & 2, patients with Category 3 prostatitis do not have any detectable infection of the prostate as determined by conventional microbiological techniques. Abnormalities in the EPS are the primary objective features of Category 3 prostatitis and chronic pain is the primary subjective symptom. The majority of patients with chronic prostatitis are Type 3(3).

[figure not shown]
The occurrence and persistence of pain as a primary presenting symptom is an important aspect of both diagnosis and outcome evaluation. In the recent review article in *Pain* by Egan and Krieger(6), they note that “chronic abacterial prostatitis is remarkably similar to chronic pain syndromes”, and accordingly they make the case for therapy based on multidisciplinary approaches to pain management, rather than the traditional ‘organ system’ approach. Many therapies have been tried for chronic prostatitis, with a primary focus on improving bladder outlet resistance. However, the general consensus among clinical urology research investigators conducting therapy trials involving chronic prostatitis patients is well reflected in the recent summary of Nickel and Sorensen(4) that

"more research and larger clinical studies in the nonbacterial chronic prostatitis syndromes are urgently required."

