2.3.2 Secondary Endpoints

A number of secondary outcome measures related to both specific symptoms and overall symptom scores will be used to supplement the analysis based on the primary endpoint. One secondary endpoint will be a participant-reported global response assessment (GRA) at six (6) weeks or withdrawal; whichever comes first, relative to overall baseline symptoms. Additional symptom-related outcome measures include the NIH-CPSI subscales and MOS SF-12.

Laboratory measures to be followed include WBC in EPS. While the true significance of WBC count in the EPS has yet to be established, it nevertheless is the primary marker of intraprostatic inflammation that can be obtained non-invasively. The exact cutoff point for deciding that inflammation is present is also controversial, with most authors relying on 10 WBC per hpf in a wet mount sample. While many investigators have pointed out the variability of WBC count in participants with CPPS over time,(8) fluctuations in the short term, such as for durations contemplated in this study, are less of a problem(9).

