10.2 Sample Size Calculations

The primary endpoint on which sample size estimates are based is the change in the overall NIH-CPSI score from baseline (randomization) to six (6) weeks. The total score has a potential range of 0 – 43 points. For each of the two primary comparisons--ciprofloxacin (CIPRO®) versus no ciprofloxacin (CIPRO®) or tamsulosin hydrochloride (FLOMAX®) versus no tamsulosin hydrochloride (FLOMAX®), we desire adequate numbers of participants to detect a difference of four (4) points in the change from baseline. We require 80% power to detect the specified difference between groups at a two-sided $\alpha = 0.05$ level of significance using a two-sample t-test. After adjustments to allow for possible dilution of statistical power due to interaction in the factorial design (50% increase), withdrawal (15% increase), clustering within Clinical Center (15% increase), a total of 184 participants or $184/4 = 46$ participants per arm will be required. Total required sample sizes for alternative differences are shown in the table below.

Δ	Trial Design	Total Sample Size using sd of change $\sigma = 6.76$
3 points	2 arms	216 (108/arm)
	3 arms	420 (140/arm)
	4 arms	644 (61/arm)
	2 x 2	324 (81/arm)
4 Points	2 arms	122 (61/arm)
	3 arms	237 (79/arm)
	4 arms	368 (92/arm)
	2 x 2	184 (46/arm)
5 Points	2 arms	80 (40/arm)
	3 arms	156 (52/arm)
	4 arms	240 (60/arm)
	2 x 2	120 (30/arm)

In addition, for each individual treatment arm of 46 subjects, the width of a 95% confidence interval for adverse event and other rates will be no wider than $\pm 15.0\%$. It is expected that these 184 participants can be accrued within approximately ten (10) months. Allowing for an additional twelve (12) weeks of follow-up on all participants, the entire study should require fourteen (14) months for completion.

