The analysis comparing the mean change in NIH-CPSI overall score from 0 to 6 weeks among treatment arms will utilize a linear regression model (equivalent to a 2-way analysis of variance) with a random effect to allow for clustering on clinical center. Standard regression diagnostics will be used to assess model adequacy and examine potential outlying or influential data points. Secondary analyses of the primary endpoint will include multivariable regression models to evaluate whether observed treatment differences, if any, can be partially accounted for by baseline differences in prognostic factors between treatment arms. Profiles of the overall NIH-CPSI score over time will also be compared among treatment groups using random effects regression models (35).

Secondary Analyses

A number of secondary analyses will be conducted, both to evaluate the secondary symptom-related outcomes and to supplement the primary endpoint comparison. Evaluation of some of the secondary outcomes will involve comparison of binary outcomes or response rates among groups. These endpoints may include the global assessment of change, change in white blood cell counts in the four-glass test, subscores of the NIH-CPSI, MOS SF12, and voiding frequency measured by a one day voiding log.

For example, one type of response will be defined based on the participant reported global assessment of change as measured at six (6) weeks or withdrawal, whichever comes first. A seven point scale will be used: 0) markedly worse; 1) moderately worse; 2) slightly worse; 3) no change; 4) slightly improved; 5) moderately improved; and 6) markedly improved. Participants who answer either 5) moderately or 6) markedly improved on this question will be considered to be responders. For this endpoint, participants who withdraw from the study for any reason (e.g. adverse events or participant choice) prior to six (6) weeks will be considered treatment non-responders. Following standard “intent-to-treat” methods, these withdrawals will be included in the denominator of the response rates for evaluation. This outcome will also serve as a validation for the primary endpoint above.

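### Rounding the three-field urine cell counts (VB1–VB3) to whole numbers discards data already read and can cost a little power on an optional secondary measure if counts are low

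*Protocol*

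**What the plan says.** Appendix F (Four Glass Test procedure, step c for the VB1, VB2 and VB3 specimens) has the microscopist examine each urine specimen at 400X and record the cell count as the "average of three fields rounded to nearest whole number". For EPS, the fourth specimen, step 5c says only "Count WBC's, RBC's, hyphae", with no averaging or rounding. Appendix C schedules the microscopy form at Screening Visit 1 and at week 6.

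Section 10.3.2 lists "change in white blood cell counts in the four-glass test" in a sentence that is worded as optional: "These endpoints may include the global assessment of change", followed by the other candidates. It adds that measures taken at baseline and one follow-up are to be compared as change from baseline, by ANOVA and regression.

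Section 2.3.2 says "Laboratory measures to be followed include WBC in EPS". It calls the cut-off for inflammation controversial, "with most authors relying on 10 WBC per hpf in a wet mount sample".

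**The concern.** Three field counts are already in hand when the value is written down, and the rule keeps only a rounded summary of them. If only that summary is recorded, no later analysis can recover the difference between no cells and one cell in three fields. Three of the four specimens behind the four-glass measure are affected, and an analysis of change takes in the rounding error at both visits.

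At stake is the precision of part of one secondary measure. With sparse counts, values pile up at zero, small means are pulled down, and a treatment effect on urine white cells is harder to detect.

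**Working it through.** **1. The plan's own figure.** The protocol gives no power, mean, SD or effect for any white-cell measure. Its only sample size rests on another endpoint: "The primary endpoint on which sample size estimates are based is the change in the overall NIH-CPSI score". A two-sample t-test with difference 4, SD 6.76, two-sided 0.05 and 80% power needs 46 per group, or 92 in total. Then 92 × 1.5 × 1.15 × 1.15 = 182.5, which rounds up to 184 in multiples of four. This reproduces the stated total, and no white-cell input enters it.

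**2. What the rule does (no assumptions).**

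| Total cells in 3 fields | Mean | Recorded |
|---|---|---|
| 0 | 0 | 0 |
| 1 | 0.33 | 0 |
| 2 | 0.67 | 1 |
| 3 | 1.00 | 1 |
| 4 | 1.33 | 1 |
| 5 | 1.67 | 2 |

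Rounding goes both ways. The only one-sided loss is at the bottom, where one cell becomes none.

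**3. Recorded values at low counts (assuming Poisson fields).** With true mean λ per field, the three-field total is Poisson with mean 3λ. Then P(any cell seen) = 1 − e^(−3λ), and P(non-zero recorded) = 1 − e^(−3λ)(1 + 3λ).

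- λ = 0.3: 1 − e^(−0.9) = 59% seen; 1 − 1.9 × e^(−0.9) = 23% recorded as non-zero.
- λ = 0.5: 78% seen, 44% recorded.
- λ = 1: 95% seen, 80% recorded.

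The mean recorded value is 0.037 at a true 0.1, 0.23 at a true 0.3, 0.46 at a true 0.5, and essentially 1.0 at a true 1. When true rates also vary between men, it is 0.25–0.26 at 0.3 and about 0.97–0.98 at 1. The downward bias is therefore confined to means below about 1 per field. It can also exaggerate a fall: a true drop from 0.3 to 0.1 (67%) is recorded as 0.230 to 0.037, and 1 − 0.037/0.230 = 84%.

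**4. Power, rounded against unrounded.** The groups are 78 against 78 (92 per factorial margin × 0.85 = 78.2), tested two-sided at 0.05. Every white-cell input is assumed.

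- A: change from baseline; between-man gamma shape 1; visit-to-visit CV 0.71 entered once; 20% fall without drug and a further 50% with drug.
- B: change from baseline; shapes 0.5–1.5; the same CV applied at each visit; 50% fall.
- C: week-6 values only, t-test; Poisson, or gamma shapes 1 and 0.5; means of 0.3 v 0.15, 0.5 v 0.3, 1 v 0.7 and 2 v 1.2.

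| Mean per field | A: unrounded v rounded | B: loss (points) | C: loss (points) |
|---|---|---|---|
| 0.3 | not run | 4–7 | 8–16 |
| 0.5 | 49% v 40% | 2–6 | 4–9 |
| 1 | 66% v 62% | 1–2 | 1–5 |
| 2 | 78% v 77% | none | under 1 |
| 4 | no loss | none | not run |

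Absolute power depends heavily on the assumed variation: at 0.5 per field with shape 1, B gave 35% v 31% where A gave 49% v 40%. The direction, and the disappearance of the loss by about 2 per field, agree across all three. A and B match the analysis of change that section 10.3.2 describes. A log-scale, baseline-adjusted analysis, which the protocol does not specify for this measure, lost more under A's inputs: 75% v 65%, 89% v 83%, 96% v 93% and 99% v 98% at means 0.5, 1, 2 and 4.

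**5. At a cut-off of 10 per high-power field.** A total of 28 gives 9.33, recorded as 9. A total of 29 gives 9.67, recorded as 10. A total of 30 gives 10 either way. Only a total of exactly 29 is reclassified.

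**The case against.** The best reply is that this hardly matters. The rule leaves out EPS, the white-cell measure that section 2.3.2 names. The four-glass endpoint is optional, and the protocol claims no power for it. Nothing shows that urine counts will be below 1 per field. If the measure were analysed as a response at 10 per field, rounding would be irrelevant. All of this stands, and it sets the severity. It does not justify the rule: no reason is given for rounding, and section 7.3 lets a man without a semen sample rely on either EPS or VB3, so VB3 can be his only prostatic specimen.

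A reader might infer three stronger things that the documents do not support.

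- *That men with visible white cells would be misclassified as non-inflammatory.* The category 3a/3b wording in the Introduction summarises a workshop classification and sets no above-zero threshold. The split is not used for eligibility, stratification or the primary analysis.
- *That rounding error is generally as large as counting error.* Under Poisson counts, the mean-square rounding error against the variance of a three-field mean is 0.060 v 0.100 at 0.3 per field, 0.072 v 0.167 at 0.5 and 0.075 v 0.333 at 1. That is 60%, 43% and 22%, before any variation between men or visits.
- *That the white-cell endpoint as a whole loses power.* EPS is outside the rule, and for VB1–VB3 the loss depends on low counts and a continuous analysis.

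**Conclusion.** The point holds as a low-severity remark on measurement precision, limited to VB1, VB2 and VB3. That one cell in three fields is recorded as none follows directly from the rule. The power cost depends on two conditions: the four-glass measure is analysed as a continuous change, and urine counts are mostly below about 1 per field. The first is plausible from section 10.3.2. The second is an assumption, because the documents give no distribution.

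Under both conditions the loss is roughly 2–9 points at 0.5 per field, 1–4 at 1 per field, and about 1 or less from 2 per field. These figures also rest on the assumed dispersion, visit-to-visit variation and drug effect. At 10 per field the effect is negligible. The primary endpoint, the total of 184 and every other stated figure are unaffected.

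**What to change.** In Appendix F, step c for VB1, VB2 and VB3, delete the instruction to round. Record the three field counts, or their total, for each urine specimen on the Four Glass Test Microscopy form at Screening Visit 1 and week 6. Analyse the unrounded mean or total.

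The cost is a small change to an existing form. The form's layout is not shown, so the number of added boxes cannot be stated. The three fields are already being read, so no extra reading, procedure or participant is needed. The change has to be made before counts are recorded, because the discarded detail cannot be restored later.

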3.3 Combination of Ciprofloxacin (CIPRO®) and Tamsulosin Hydrochloride (FLOMAX®)

The etiology and pathogenesis of pain and voiding dysfunction in men with CPPS are not known and are likely multi-factorial. For instance, chronic infection may lead to irritation of muscles at the bladder neck, which might persist even after eradication of the infection. Alternatively, recurrent infection may be caused by persistence of residual urine in men with dysfunctional voiding. The rationale for the combination of ciprofloxacin and tamsulosin hydrochloride therefore is to 1) attempt to maximize eradication of bacteria by improving bladder emptying, 2) improve both pain and voiding symptoms, regardless of etiology and 3) gain insight into the pathophysiology of CPPS by comparing pretreatment culture and voiding parameters with response to medications.

In a retrospective, nonrandomized study, the combination of alpha blockers and antibiotics were superior to antibiotics alone in men with chronic bacterial prostatitis(27). For men with nonbacterial prostatitis, alpha-blockers were superior to antibiotics for improving symptoms. The combination of agents was well tolerated with no unique side effects seen. Indeed, there is

no mechanistic reason to suppose that a fluoroquinolone such as ciprofloxacin would interact with a selective alpha-1 blocker such as tamsulosin hydrochloride.

With regard to the pathogenesis of symptoms, one hypothesis to be tested is whether participants with urinary symptoms plus pain are somehow different from those with pain alone. If participants with pain alone, without voiding symptoms, respond to tamsulosin hydrochloride in the same way those with voiding symptoms, then the beneficial actions may be centrally mediated. If only participants with voiding symptoms respond to tamsulosin hydrochloride, then the action may be either central or at the end organ level. Similarly, it will be important to correlate any response to ciprofloxacin (CIPRO®) with the presence of bacterial growth in the prostate or urine for micro-organisms, especially bacteria considered to be “non-pathogens” such as gram positive bacteria. If eradication of bacteria is associated with an improvement of symptoms, then a pathogenic role is suggested. If improvement is seen regardless of culture status, then a direct anti-inflammatory role of the antibiotic would be likely.

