7.3 Screening Visit #2

Participants who still meet all eligibility criteria at this visit will complete the questionnaires and/or undergo the examinations described below, and will continue on to randomization (Section 7.4).

1. *Eligibility Checklist*.

An eligibility checklist confirming that the participant still meets all eligibility criteria will be completed by the RC prior to randomization.

2. *Demographic Questionnaire.*

Each participant will provide the research staff with his demographic information, including date of birth (age), race, marital status, socioeconomic status, level of education.

3. *Concomitant Medications.*

The research staff will record the medications currently being taken by the participant. Participants will be asked to recall their medications if they fail to bring them to the second screening visit.

4. *Participant Symptom/Impact/General Quality of Life Index.*

Each participant will provide the research staff with an assessment of his discomfort/pain by completing the NIH-CPSI. In addition, participants will complete the MOS SF-12, a general Quality of Life Index.

5. *1-day Voiding Log Supplies and Directions.*

A 24-hour voiding log will be collected and reviewed for completion for each participant.

6. *Uroflow and Post Void Residual.*

Participants will undergo urodynamic testing at screening visit #2. The research staff will measure and record participants total voided volume, peak flow, average flow and post-void residual.

7. *Semen Sample Collection.*

A semen sample will be collected and cultured for localized pathogens. Participants are permitted to refuse to provide a semen sample. It is also acceptable if a participant is unable to provide a semen sample. However, participants not providing a semen sample, for whatever reason, must have provided at least one of either an EPS or VB3 sample during screening visit #1.

8. *Medication Diary.*

Participants will be required to maintain a medication diary to record any changes in medication. Participants will also be asked to record all possible adverse events.

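### Appendix F cleanses before the four-glass cultures but not before the semen culture, and the baseline and week-6 semen samples are not collected alike: a cheap improvement that bears on an exploratory question only

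*Protocol*

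**What the plan says.** **Four-glass test (Appendix F, steps 1-3).** The participant retracts the foreskin if uncircumcised. Step 2 is "Wipe head of penis with one alcohol pad". Only then comes step 3, "Collect the first 10 ml sample (VB1) directly into sterile container". VB1 and VB2 are both passed before prostatic massage. Section 7.2 has the EPS and VB3 findings compared with VB1 and VB2.

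**Semen sample (Appendix F, steps 1-4).** Step 1 is "Instruct participant to remain abstinent for a minimum of two days" and step 2 is "Collect specimen in a sterile urine cup". Volume is then measured, and the sample is plated on blood and MacConkey agar and cultured for five days. No cleansing or voiding line appears, and no comparison with VB1 or VB2 is stated for semen.

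**Use of the semen culture.** Section 7.3, item 7: "A semen sample will be collected and cultured for localized pathogens". The same item makes an EPS or VB3 sample compulsory only for men who give no semen. Section 7.6 restricts week-6 semen to men with localized uropathogens at baseline. The footnote to the semen procedure ties this to baseline visit 2 and schedules the repeat sample 2-3 days after Visit 4.

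**Scientific question.** Section 3.3 considers it important to "correlate any response to ciprofloxacin (CIPRO®) with the presence of bacterial growth in the prostate or urine", and singles out gram-positive organisms usually regarded as non-pathogens.

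**The concern.** The protocol treats cleansing as part of a proper localization culture for one specimen and omits it for another that serves a related purpose. Semen passes through the urethra and over the glans. A site that follows Appendix F exactly will therefore culture a specimen open to surface contamination that the four-glass procedure takes steps to limit.

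Two things are at stake. First, men without prostatic organisms could be placed in a culture-positive group. If surface organisms are mainly gram-positive (my assumption; the documents do not say), they would fall in the very class that section 3.3 wants to study. Blurring the two groups shrinks any real difference in ciprofloxacin response between them. Section 3.3 reads improvement regardless of culture status as pointing to a direct anti-inflammatory action, so dilution would lean towards that reading. Second, section 3.3 also reasons from eradication of bacteria. That needs baseline and follow-up specimens collected in the same way, and they are not.

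**Working it through.** The plan gives no figure on this point, so the check is mainly a comparison of the text.

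**1. Collection steps side by side**

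| Step before or at collection | Four-glass test | Semen, Visit 2 | Semen, 2-3 days after Visit 4 |
|---|---|---|---|
| Foreskin retraction | yes | not stated | not stated |
| Alcohol wipe | yes | not stated | not stated |
| Void before the prostatic specimen | yes (VB1, VB2) | yes, by order of procedures | not stated |
| Stated comparison with VB1/VB2 | yes (EPS, VB3) | not stated | not stated |

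The Visit 2 void follows from two places. Section 5.5 says that sections 7.2 and 7.3 list procedures in the order in which they are done, and section 7.3 puts uroflow (item 6) before semen (item 7). Appendix F asks for at least 150 cc for a valid uroflow test. The repeat sample comes on a separate day with no procedure listed before it.

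**2. Timing of the comparator.** Appendix C schedules four-glass cultures at Visit 1 and week 6 only. Visit 2 is one to three weeks after Visit 1. Semen is the only culture specimen at Visit 2, so the nearest baseline VB1 and VB2 are one to three weeks older.

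**3. Illustration of dilution.** Every rate here is assumed: true prostatic growth p = 20% (range 10-30%), culture sensitivity s = 90%, false growth from contamination in c = 10%, 30% or 50% of truly negative men, and semen as the only classifier. The true difference in ciprofloxacin effect between culture-positive and culture-negative men is set at 4 points. (Section 10.2 uses 4 points for a main effect, not for this interaction.)

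- PPV = sp / [sp + c(1 - p)]
- NPV = (1 - c)(1 - p) / [(1 - c)(1 - p) + (1 - s)p]
- Apparent difference = 4 × (PPV + NPV - 1)

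| c | PPV | NPV | Apparent difference |
|---|---|---|---|
| 10% | 0.18/0.26 = 0.692 | 0.72/0.74 = 0.973 | 4 × 0.665 = 2.7 |
| 30% | 0.18/0.42 = 0.429 | 0.56/0.58 = 0.966 | 4 × 0.394 = 1.6 |
| 50% | 0.18/0.58 = 0.310 | 0.40/0.42 = 0.952 | 4 × 0.263 = 1.05 |

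The extremes are 4 × 0.145 = 0.6 (p = 10%, c = 50%) and 4 × 0.749 = 3.0 (p = 30%, c = 10%).

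These rows are not the gain from cleansing, because a wipe need not remove all contamination. If it lowered c from 30% to 10%, the apparent difference would rise from 1.6 to 2.7, a gain of 1.1 points. If it changed nothing, the gain would be zero.

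**4. How much the comparison could carry anyway.** Take 184 × 0.85 = 156 evaluable men, SD 6.76 (section 10.2), 20% culture-positive without error, and each culture group split equally by ciprofloxacin. The standard error of the interaction is 6.76 × √(4/31.2 + 4/124.8) = 2.71. For a 4-point interaction, 4/2.71 - 1.96 = -0.48, which gives power just over 30%. The comparison is exploratory even with perfect cultures.

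**The case against.** **The baseline sample already follows a void.** A reader might infer from the semen steps alone that neither sample is preceded by voiding. The order fixed by sections 5.5 and 7.3 does not support that for baseline. This part of the objection stands, and the voiding gap is confined to the week-6 sample.

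**Nothing says that any semen growth counts as localized.** A reader might infer that contaminants are automatically scored as prostatic infection. The text speaks of localized pathogens and uropathogens, which is narrower than growth, and section 3.3 treats gram-positive non-pathogens separately. The protocol leaves open how semen growth is interpreted; it does not adopt a rule that counts contaminants. This also stands.

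**Semen is not the sole classifier.** Section 3.3 speaks of prostate or urine and does not name semen. The four-glass test is attempted in every man, after cleansing. The illustration therefore overstates dilution for men who have usable EPS or VB3 cultures. The documents do not give the share of men for whom semen is the only prostatic-tract specimen.

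**The question is peripheral.** Culture status is not among the endpoints in section 2.3, and section 10.3.2 describes no analysis by culture status. Baseline contamination arises before randomization and so is unrelated to arm.

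**The Manual of Procedures may cover it.** Section 9.3 places operating procedures there, and it is not at hand. But Appendix F is itself a step-by-step procedure, spells out cleansing for one specimen and not the other, and does not refer to the Manual here.

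**Conclusion.** The concern holds as a cheap improvement. Appendix F omits for semen the cleansing that it requires for the four-glass cultures, and the baseline and week-6 semen samples differ in whether a void precedes them. The possible consequence is dilution of the exploratory comparison in section 3.3, and some effect on which men are asked for week-6 semen.

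The size cannot be derived from the documents. The range of 0.6 to 3.0 points for a true 4-point difference rests on assumed prevalence, sensitivity and contamination rates, on semen as the only classifier, and on comparison with an error-free culture. It shows direction and is not an estimate.

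A reader might infer that the trial's efficacy result is at risk. The documents do not support that: the primary NIH-CPSI comparison and the global response assessment do not use culture status, so neither is affected.

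**What to change.** In Appendix F, Semen Sample Procedure:

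1. Insert four-glass steps 1 and 2 (foreskin retraction and alcohol wipe) ahead of semen step 2, for both the Visit 2 sample and the sample after Visit 4.
2. State that the participant voids before collection on both occasions. At Visit 2 the uroflow void already serves. For the later sample this is a new line, and it makes the two collections match.

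As a supporting analysis rule, interpret semen growth against the same man's VB1 and VB2 cultures: Visit 1 for baseline, Visit 4 for week 6. Acknowledge that the baseline urines are one to three weeks older than the semen and the week-6 urines 2-3 days older. The rule is a partial safeguard and does not replace clean collection.

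The cost is one alcohol pad and two instruction lines per sample. No extra visit or culture is needed.
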